Chronic obstructive pulmonary disease (COPD) is a lung disease that tends to affect older adults. Breathlessness is the most common symptom which greatly impairs quality of life. COPD is mainly treated using inhalers taken once-or-twice every day, but another type of inhaler, called a short-acting beta agonist (SABA), is only meant to be used when needed to provide short-term symptom relief. People with COPD often don't know how best to manage their breathlessness and can become reliant on their SABA, using it too often, risking side effects. Those with COPD that use their SABA frequently have worse breathlessness and are more likely to have COPD 'flare-ups'. We believe that teaching COPD patients how to use a hand-held-fan (HHF), and other techniques to manage their breathlessness (the FanFIRST intervention), may improve their breathlessness and reduce how often they need their SABA. SABA inhalers contain a strong greenhouse gas that contributes to global warming. Therefore, reducing how many SABA inhalers are used each year has potential dual-benefits to both COPD patients and the environment.

The FanFIRST intervention takes about 10-minutes and includes providing a fan and teaching people how to use it, alongside guidance on positions and breathing techniques to help manage breathlessness. Written information about breathlessness and anxiety and how to manage this will also be provided.

A large trial is needed to tell if the FanFIRST intervention can help people manage their breathlessness and reduce SABA inhaler use. But, before we start, there are a number of questions which need to be answered. For example:

- Can we recruit enough people to a trial?
- What sort of health services are best to recruit people from?
- Do people like the FanFIRST intervention; and What do people with COPD (and their carers) think about the trial design, and the questions that it is designed to answer?

To answer these questions and more, we will first undertake a smaller study called a feasibility trial. We will invite 80 people with COPD that use their SABA inhaler frequently. Eligible participants will be chosen at random to receive either the FanFIRST intervention, or usual care. Regardless of study condition, all participants will be given devices that attach to their SABA inhaler to count how often they are used. We will measure usage throughout the study and compare use at the start of the study

| Confidential | | Protocol | | | | |
|--------------|-------------|--------------------------|--------------|--|--|--|
| Connachtai | IRAS 318320 | Version No. 1.1 29.08.23 | Page 3 of 57 | | | |

with usage at the end of the study. People will take part for 4 months in total, with breathlessness questionnaires and other measures completed every 28 days during the study. A total of 40 participants (and their carers) will also be invited to take part in an interview with a researcher.

The results of the feasibility study will tell us two important things. First, whether a larger trial is possible, and if so, how best to run it. Second, if provisional results are deemed effective, how best to roll-out the FanFIRST intervention across the NHS.

| Confidential |
|--------------|
|--------------|

Protocol Version No. 1.1 29.08.23

Page 4 of 57

PROTOCOL SYNOPSIS

IRAS 318320

| Sponsor | Hull University Teaching Hospitals NHS Trust |
|-------------------------|---|
| Intervention | A brief (deliverable in 10 minutes), complex breathlessness intervention comprising provision of a rechargeable hand-held fan (HHF). Also provided as part of the intervention are verbal and written instructions in its use, guidance on positions/breathing techniques and exercises to relieve breathlessness; and written information about managing anxiety to improve breathlessness. |
| Study Number | IRAS ID: 318320 Funder Reference: NIHR204349 |
| Title of Study | Fan Feasibility Randomised Controlled Trial (RCT) for people living with COPD and high SABA intake (FanFIRST) |
| Study Centres | Castle Hill Hospital, [name] Holderness Health, St Nicholas Surgery, [name] Bradford Teaching Hospitals NHS Foundation Trust, [name] The Bloomsbury Surgery, [name] |
| Phase of Development | Feasibility |
| Aims and Objectives | Aim We will: Assess the feasibility and optimal design for a Phase-3, RCT comparing HHF-based breathlessness management (FanFirst intervention) with usual care in people with COPD and high SABA use, and Explore barriers and facilitators to NHS-wide implementation of the FanFIRST intervention. Objectives order to achieve the study aims, the study is designed to address uncertainties regarding: Feasibility of recruiting participants and collecting sufficient outcome and implementation data Baseline measure variability to enable sample-size estimation for the future Phase-3 trial Intervention delivery with fidelity Relevance and acceptability of the intervention and proposed outcomes to participants and clinicians |

| Confidential | Protocol | | | | |
|--------------|-------------|--------------------------|--------------|--|--|
| Connacitiai | IRAS 318320 | Version No. 1.1 29.08.23 | Page 5 of 57 | | |

| Study Design | 5. How different settings characteristics constrain or enable implementation, and their implications for intervention flexibility and development of an implementation strategy A multicentre, parallel-group, open-label, randomised controlled, hybrid Type-I effectiveness-implementation feasibility study of the FanFIRST intervention in COPD patients with high SABA-use. A schedule of assessments and procedures is provided in Table 1. A flow chart of the study is provided in Figure 1. | | |
|--|--|--|--|
| Number/Type of Participants | Eighty eligible, consenting people with COPD and high SABA-use in the year prior to recruitment. | | |
| Inclusion Criteria | Adults aged ≥30 years Clinician diagnosed COPD with airflow obstruction, confirmed on spirometry (FEV-1/FVC ratio <0.7) Current or ex-smokers with ≥10 pack-year smoking history Modified Medical Research Council Dyspnoea Scale (mMRC) breathlessness score ≥2 Patients receiving optimal guideline recommended inhaled treatment for COPD, including a minimum of dual-acting bronchodilator therapy (long-acting beta-agonist and long-acting muscarinic antagonist) with or without an inhaled corticosteroid. Patients prescribed ≥12 SABA inhalers/canisters within the past year with self-reported SABA use most days. Only those prescribed a pressurised metered dose inhaler (pMDI) SABA are eligible for inclusion. Provision of written informed consent Willing and able to comply with all required study activities | | |
| Exclusion Criteria | Those with significant cardiorespiratory disease, other than COPD, considered the primary cause of their breathlessness/high SABA use. Those with a COPD exacerbation requiring oral corticosteroids and/or antibiotics and/or hospitalisation within 4-weeks before recruitment (taken from last day of exacerbation treatment). Those with a planned pulmonary rehabilitation attendance during the study (pulmonary rehabilitation referral will be offered one on completing trial participation if appropriate). | | |
| Study Treatment(s) | Participants will be randomised to receive either 1. FanFIRST intervention plus usual care, or 2. Usual care without the FanFIRST intervention. | | |
| Study Endpoints and Statistical Methods | Feasibility Feasibility outcomes will be assessed against stop-go/traffic-light criteria (underlined and detailed in Box.1) for definitive trial progression: | | |

| Confidential | Protocol | | | | |
|--------------|-------------|--------------------------|--------------|--|--|
| Connacinal | IRAS 318320 | Version No. 1.1 29.08.23 | Page 6 of 57 | | |

| Sample Size Rationale | Since this is a feasibility study, a formal sample-size calculation has not been performed. We will recruit 80 patients over 12 months. |
|-----------------------|---|
| Safety Analyses | AEs/SAEs will be listed and summarised using descriptive statistics |
| | The feasibility of collecting health economic data will be evaluated to inform aspects for full health economic evaluation in the definitive trial. |
| | Health Economics |
| | All adverse events (AEs) and serious adverse events (SAEs) will be recorded |
| | Safety |
| | COPD Assessment Test (CAT) score Breathlessness numerical rating scales for 'worst', 'distress caused by' and 'coping with' breathlessness within the past 24 hours Modelled annual SABA inhaler/cannister pick-up rate (based on number of actuations at baseline (days -28 – 0) and between days 56 and 84) Health-related quality-of-life: EQ-5D-5L and VAS Healthcare-resource-utilisation Modelled CO2e (for COPD treatments alone and combined for COPD treatments, study intervention and healthcare-resource-utilisation). |
| | The proposed primary outcome is change in mean daily SABA use from baseline (days -28-0) at days 56 - 84. Smart inhaler technology supplied by Propeller Health, USA, will objectively count SABA actuations each day. Baseline data will inform intra- and inter-individual SABA use variability, as well as provide an optimal monitoring duration for the definitive trial. Daily SABA use will be recorded throughout the trial to enable evaluation of change in use and any potential degradation of intervention effect over-time. Secondary Outcomes |
| | Efficacy Primary Outcome |
| | Recruitment and retention: recruitment rate (per site and aggregated), eligibility to consent ratio, screen failures and participant retention. Data quality and integrity: Amount and pattern of missing data (SABA inhaler use) Outcomes: acceptability of proposed outcomes (qualitative interviews) and integrity of outcome data Intervention: feasibility, acceptability and fidelity of the intervention will be assessed |

| Confidential | Protocol | | | | |
|--------------|-------------|--------------------------|--------------|--|--|
| Connacinal | IRAS 318320 | Version No. 1.1 29.08.23 | Page 7 of 57 | | |

Table 1 Schedule of Assessments and Procedures

[figure not shown]
| Visit | Consent/ Screening Start of baseline | Baseline Visit End of baseline | | Study Visit 1 (Face-to- or remot | | Study Visit 2 (Face-to or remo | -face | Study Visit | • |
|--|---|---|-----------------------|---|-----|---|-------|----------------|----------|
| Day | -28 | 0 | | 28 days) | (±3 | 56 days) | (±3 | 84 days | (±3) |
| Procedure/Assessment | | | | | | | | | |
| Inclusion/exclusion criteria | х | | | | | | | | |
| Written Informed Consent | х | | | | | | | | |
| Medical History | х | | | | | | | | |
| Vital signs | х | x | | | | | | х | |
| Weight and Height | х | | | | | | | х | |
| Physical Examination | > | (* | | | | | | | |
| Spirometry | > | ر ۸ | | | | | | | |
| AE Monitoring | х | х | | х | | Х | | х | |
| Inhaler technique assessment | х | | | | | | | | |
| SABA Use Monitoring | х | x | | х | | х | | х | |
| Breathlessness NRSs | х | x | | х | | х | | х | |
| CAT Score | x | x | | x | | x | | х | |
| mMRC | х | | | | | | | | |
| EQ5D-5L | х | x | () | | | | | х | |
| Invitation Experience survey | х | | Day | | | | | | |
| Healthcare resource Utilisation | | х | n (I | х | | х | | х | |
| Qualitative Interviews | | | tio | | | | | х | |
| Evaluation of usual care received since last visit** | | x | Randomisation (Day 0) | x | | х | | х | |
| Randomisation | | х | pu | | | | | | |
| Study Experience Survey | | | Ra | | | | | х | |

CAT: COPD Assessment Test, mMRC: modified Medical Research Council, NRS: Numerical Rating Scale, EQ-5D-5L: EuroQual 5 dimensions 5 level.

Schedule of events * Physical examination to be performed on 1 occasion during screening (on either day -28 or day 0 visit prior to randomisation). **Usual care received will be evaluated following each study visit to capture i) new treatments initiated, ii) changes to pre-existing COPD treatment and iii) self-management interventions undertaken since the last visit. A standardised questionnaire using non-leading questions will be used to capture elements of non-pharmacological breathlessness self-management used by each group. ^ Spirometry should be done during the screening visit where possible, but can be done anytime between the screening and baseline visit, in accordance with local capacity/infection control procedures. ^^ Participants that have linked their smart inhaler sensor to their smartphone, enabling remote assessment of sensor function and recording, can have visits 1 and 2 undertaken remotely (via telephone).

| Confidential | Protocol | | | | |
|--------------|-------------|--------------------------|--------------|--|--|
| Connacintal | IRAS 318320 | Version No. 1.1 29.08.23 | Page 8 of 57 | | |

Figure 1 Study Flow Chart

| Confidential | Protocol | | | | |
|--------------|-------------|--------------------------|--------------|--|--|
| Connacinal | IRAS 318320 | Version No. 1.1 29.08.23 | Page 9 of 57 | | |

CONTENTS

| PLA | IN EN | NGLISH SUMMARY | 2 |
|-----|-------|--|----|
| PRC | отос | OL SYNOPSIS | 4 |
| | Tab | ble 1 Schedule of Assessments and Procedures | 7 |
| | Figu | ure 1 Study Flow Chart | 8 |
| 1. | BAC | CKGROUND AND RATIONALE | 12 |
| 2. | STU | JDY AIMS AND OBJECTIVES | 13 |
| 3. | STU | JDY DESIGN | 14 |
| 3 | .1 | Patient and public involvement | 14 |
| 3 | .2 | Study Sites | 15 |
| 4. | STU | JDY POPULATION | 15 |
| 4 | .1 | Inclusion Criteria | 15 |
| 4 | .2 | Exclusion Criteria | 16 |
| 4 | .3 | Participant Identification and Screening | 16 |
| 4 | .4 | Participant Withdrawal | 17 |
| 5. | STU | JDY INTERVENTION | 18 |
| 5 | .1 | Summary | 18 |
| 5 | .2 | FanFIRST Intervention Delivery | 18 |
| 5 | .3 | Intervention Fidelity | 18 |
| 6. | 001 | TCOMES AND MEASURES | 20 |

1. BACKGROUND AND RATIONALE

Over-reliance on short-acting beta agonist inhalers (SABA) in COPD can reflect uncontrolled breathlessness, can cause side effects (tremor/palpitations), and is harmful to the environment. We will conduct a feasibility randomised controlled trial (RCT) of a simple and scalable breathlessness management intervention in COPD patients who over-use SABA to investigate i) the feasibility and optimal design of a definitive trial investigating the potential to improve symptom control and reduce SABA reliance in COPD, and ii) explore factors impacting wide-scale adoption of our intervention across the NHS.

SABA are the most prescribed inhalers in England. They relax airway smooth muscle, temporarily relieving symptoms caused by airway narrowing (bronchospasm). However, SABA over-use is linked with poor patient outcomes and environmental damage.

High SABA use is well delineated in asthma where it is associated with exacerbation risk, health-careresource utilisation and excess mortality^{1,2}. Although less studied, high SABA use in COPD is associated with worse quality-of-life and exacerbation risk^{3,4,5}; events that drive disease progression and mortality⁶⁻⁸. Where policy and guidelines are helping drive down SABA use in asthma, less is known about how to achieve this in COPD.

COPD typically affects older adults and is associated with deprivation. Breathlessness is common in COPD⁹, impairs quality-of-life¹⁰, physical and social function¹¹, and leads to dependence on health services^{12,13}. Breathlessness causes vicious cycles of activity avoidance, deconditioning, and anxiety-panic, worsening breathlessness¹⁴. Optimal symptom and disease-control is therefore crucial in COPD. However, despite availability of evidence-based, non-pharmacological breathlessness interventions such as the hand-held fan (HHF)^{15,16}, pharmacological strategies such as SABA are often prioritised, risking over-use and over-reliance.

SABA's role in managing daily variations in chronic breathlessness in COPD is poorly understood⁴ with people with COPD typically already established on long-acting bronchodilators¹⁷. Managing major symptom components with the HHF and addressing unhelpful breathing patterns and anxiety, may be more effective than, and reduce, SABA use.

~94% of the 21 million SABA prescribed in England each year are greenhouse gas containing metered dose inhalers¹⁸. Consequently, SABA account for 70% of the UK's inhaler-related carbon footprint, totalling 863 kilotonnes CO₂e annually¹⁹. Mitigating the health risk from climate change is a World

| Confidential | | Protocol | |
|--------------|-------------|--------------------------|---------------|
| Connacinal | IRAS 318320 | Version No. 1.1 29.08.23 | Page 13 of 57 |

Health Organisation (WHO) global priority²⁰. Where primary care contracts previously incentivised reducing SABA over-reliance in asthma, with quality improvement programmes developed to achieve this²¹, no such incentives or interventions exist in COPD. There is therefore an unmet need for evidence-based interventions to achieve this important goal.

We will undertake a feasibility, randomised controlled trial of HHF-based breathlessness management (the FanFIRST intervention) in COPD patients with high SABA use to assess the feasibility and optimal design of a definitive trial to evaluate the impact of the FanFIRST intervention on SABA use, symptoms, quality of life, health care resource utilisation, environmental impact, safety and cost effectiveness. Our proposed feasibility trial will address uncertainties relating to fundamental trial elements, thereby favouring a stand-alone feasibility trial rather than an internal pilot. Taking an overall effectiveness research perspective²², our feasibility study incorporates a theory-based approach to assess how processes, impact mechanisms and contextual factors shape outcomes. If proven effective, the FanFIRST intervention would be the first evidence-based, implementation-ready intervention to reduce SABA over-reliance in COPD with both patient and environmental benefits. The simple and scalable nature of the intervention means that FanFIRST has significant potential to lead to a step change in the way that breathlessness and high SABA use is managed in COPD.

2. STUDY AIMS AND OBJECTIVES

Aims

The aims of the study are to:

- i. Assess the feasibility and optimal design for a phase-3, RCT comparing HHF-based breathlessness management (FanFirst intervention*) with usual care in people with COPD and high SABA use, and
- ii. Explore barriers and facilitators to NHS-wide implementation of the FanFIRST intervention.

*The FanFIRST intervention is a brief (deliverable in 10 minutes), complex breathlessness intervention comprising provision of a rechargeable HHF. Verbal and written instructions in the HHFs use, positions/breathing techniques and exercises to relieve breathlessness; and written information about managing anxiety to improve breathlessness, are also provided as part of the intervention.

| Confidential | Protocol | | | | | |
|--------------|-------------|--------------------------|---------------|--|--|--|
| Connacinal | IRAS 318320 | Version No. 1.1 29.08.23 | Page 14 of 57 | | | |

Objectives

In order to achieve the study aims the study is designed to address uncertainties regarding:

- 1. Feasibility of recruiting participants and collecting sufficient outcome and implementation data.
- 2. Baseline measure variability to enable sample size estimation for the future Phase-3 trial.
- 3. Intervention delivery with fidelity.
- 4. Relevance and acceptability of the intervention and proposed outcomes to participants and clinicians.
- 5. How different settings characteristics constrain or enable implementation, and their implications for intervention flexibility and development of an implementation strategy.

3. STUDY DESIGN

Multicentre, parallel-group, open-label, randomised controlled, hybrid Type-I effectivenessimplementation feasibility study. Patients will be randomised to either usual care or the FanFIRST intervention in a 1:1 ratio using random permuted blocks. Randomisation will be stratified by site and based on self-reported HHF usage (any reported HHF-use) within the past month.

Taking an overall effectiveness research perspective, consistent with the MRC's updated framework for developing and evaluating complex interventions²²²², the study incorporates a theory-based approach to assess how processes, impact mechanisms and contextual factors shape outcomes²³²³²³.

3.1 Patient and public involvement

The study design, intervention and documents have been informed by a dedicated FanFIRST patient and public involvement (PPI) group. The Patient Advisory Group is made up of four members and includes patients and carers who have experience living with, or caring for somebody with, COPD and/or chronic breathlessness. All PPI group members are members of Involve Hull; a network developed to ensure that patients and their carers are empowered to have the opportunity to shape research. The FanFIRST PPI Group was formed using funding from the University of Hull and convened prior to the Stage 1 submission. Following success at Stage 2, two more experienced PPI members have been recruited to join the Trial Management Group and a further two to join the Trial Steering Committee. Further detail on both of these groups is provided in Section 12.

| Confider | Confidential | | Protocol | |
|----------|--------------|-------------|--------------------------|---------------|
| | Connacitiai | IRAS 318320 | Version No. 1.1 29.08.23 | Page 15 of 57 |

3.2 Study Sites

The trial will recruit from four National Health Service (NHS) study sites. A list of the sites can be found in the Investigator Team section on page 3. In addition, where requested by study sites, a participant identification centre (PIC) will be used to identify suitable study participants (see PIC site already identified on page 3).

4. STUDY POPULATION

Eighty eligible consenting people with COPD and high SABA-use[^] during the year prior to study recruitment. Participants that do not meet all of the eligibility criteria will not qualify for enrolment. A study screening and enrolment log will be kept to include all potential participants sent a participant information sheet, recording reasons for ineligibility when applicable. All consenting participants will be provided with an automatically generated subject identification number (SIN) and enter study screening. For participants that do not pass screening, reasons for failure will be recorded on the screening log and within REDCap.

[^]For this study, high SABA-use will be defined as 12 or more SABA prescriptions issued during the prior 12-months with self-reported SABA-use most days.

4.1 Inclusion Criteria

- Adults aged ≥30 years
- Clinician diagnosed COPD with airflow obstruction, confirmed on spirometry (FEV-1/FVC ratio <0.7)
- Current or ex-smokers with ≥10 pack-year smoking history
- Modified Medical Research Council Dyspnoea Scale (mMRC) breathlessness score ≥2
- Patients receiving optimal guideline recommended inhaled treatment for COPD, including a minimum of dual-acting bronchodilator therapy (long-acting beta-agonist and long-acting muscarinic antagonist) with or without an inhaled corticosteroid.
- Patients prescribed ≥12 SABA inhalers/canisters within the past year with self-reported SABA use most days. Only those prescribed a pressurised metered dose inhaler (pMDI) SABA are eligible for inclusion.
- Provision of written informed consent
- Willing and able to comply with all required study activities

| Confidential | Protocol | | | | | |
|--------------|-------------|--------------------------|---------------|--|--|--|
| Connacitiai | IRAS 318320 | Version No. 1.1 29.08.23 | Page 16 of 57 | | | |

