Participants that fail screening on first attempt will be eligible for re-screening, provided the reason for screen failure is resolved prior to completion of study recruitment. This does not apply to cases where screen failure is related to SABA-use during the prior 12-months being below the threshold for study inclusion. In these case, re-screening will not be permitted. Those participants who become eligible following re-screening will be assigned with a new SIN. Participants that screen fail will be replaced.

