7.1.4 Consent/Screening Visit

- Participants will be invited to attend their local study site on day -28. Consent and enrolment (subject to non-failure of screening points) will take place as outlined in Table 1. During this visit, participants' inhaler technique will be assessed and training provided as required. Participants will be asked to bring their SABA inhaler(s) with them to the screening visit (included in PIS and during visit booking).
- Consent and Enrolment
- Eligibility assessment against criteria. See Table 4 for day -28 requirements and screen-fail points (SFP)
- The Participants SABA inhaler prescription and their SABA inhaler, brought to the screening visit, will be reviewed in order that the appropriate Propeller Sensor can be issued. If a participant's SABA is prescribed by the generic drug name (e.g. salbutamol pMDI) rather than brand (e.g. Ventolin Evohaler or Salamol pMDI), the participant should be provided with a Study SABA Information Card (SAIC). The study clinician will write the name of the SABA branded device that the patient brought with them to the SAIC. Participants will be instructed to show the SAIC to the pharmacist when they collect any new SABA prescriptions and thus ensure that they are issued with the same SABA for the duration of the study. This will enable the easy transfer of the provided Propeller Sensor(s) to any replacement inhalers.
- Provision of and training in the use of the Propeller Sensors for SABA monitoring.

Table 4 Day -28 processes and SFPs

| Medical History ⁺ | Questionnaires | Medical tests/Equipment |
|---|----------------------------|---------------------------------------|
| | | provision |
| SFP1: If FEV-1/FVC ratio >0.7 on screening spirometry. Check and record results of last | • mMRC. SFP8: Score <2 | Vital signs: (Body Temperature, |
| recorded historical Spirometry for all participants | Breathlessness Numerical | Pulse Rate, Respiration Rate, Blood |
| | Rating Scale (NRS) | Pressure) |
| SFP2: If pulmonary rehabilitation is planned to occur during study participation, are | COPD Assessment Test (CAT) | |
| they happy to wait to receive post-study? | • EQ-5D-5L Quality of life | Height, weight and BMI |
| SFP3 : Is significant cardiorespiratory disease, other than COPD, considered the primary | questionnaire | Start SABA-use monitoring: |
| cause of their breathlessness/high SABA use? | Patient Feedback | Participants will be provided with |

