| cause of their breathessnessynigh SADA use: | Questionnaire* | the Propeller sensors to apply to |
| SFP4: Has a COPD exacerbation requiring oral corticosteroids and/or antibiotics and/or | | their prescribed SABA inhalers. |
| hospitalisation occurred within 4-weeks before recruitment (taken from last day of | | Training on their usage will be |
| exacerbation treatment). Record number of COPD exacerbations for the last 12 | | provided onsite, with written |
| months, including dates, treatments received, and whether ED attendance and/or | | instructions to also be provided. |
| hospitalisation occurred | | Participants who will not be using |
| | | the app will have their sensor |
| SFP5a: Does participant self-report <daily saba="" td="" use?<="">	synced onsite through a site specific	</daily> | | synced onsite through a site specific |
| | | app. |
| SFP5b:Have they had <12 SABA inhalers/canisters prescribed within the past year. | | app. |
| Record Name, dose and number of prescriptions within the past 12-months for all | | Provide a 'Study SABA Information |
| | | Card'(SAIC) if the participant's |

| Medical History ⁺ | Questionnaires | Medical tests/Equipment |
|---|----------------|----------------------------------|
| | | provision |
| inhaled medications. Note the current SABA prescription and confirm that it is a | | SABA is prescribed using the |
| pressurised metered dose inhaler (pMDI). | | generic drug name rather than by |
| SFP6: Have they been receiving optimal guideline recommended inhaled treatment for COPD^? | | brand. |
| Smoking status. SFP7 : <10 pack per year smoking history (see questionnaire section for SFP8) . | | |
| History of HHF use: | | |
| Question 1: 'Have you used the HHF in the past month – Yes/No. If 'Yes' is ticked, | | |
| follow up question 'How often 1) Every day, 2) Most days, 3) Occasionally or rarely | | |
| Record of Health Care Resource Use in the past 4-weeks. See section 7.4.3 for details of this | | |

^Optimal treatment is defined as a minimum of dual-acting bronchodilator therapy (long-acting beta-agonist and long-acting muscarinic antagonist) with or without an inhaled corticosteroid.

[†]In addition, to the information collected in Table 4, the following demographic information will be collected: age, gender, ethnicity, socioeconomic status [obtained from postcode], educational attainment

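### Section 4.1 admits SABA use on most days, but Table 4 (SFP5a) screen-fails anyone reporting less than daily use

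*Protocol*

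**What the plan says.** **Inclusion criterion.** Section 4.1, and the synopsis in the same words: "Patients prescribed ≥12 SABA inhalers/canisters within the past year with self-reported SABA use most days".

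**Definition of the population.** Section 4, footnote: "high SABA-use will be defined as 12 or more SABA prescriptions issued during the prior 12-months with self-reported SABA-use most days". Section 4 also says that anyone who does not meet every criterion does not qualify.

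**Screening list.** Section 7.1.4 sends sites to Table 4 for what to check at day -28. On frequency, the item opens "SFP5a: Does participant self-report <daily" and goes on to SABA use. On quantity: "SFP5b:Have they had <12 SABA inhalers/canisters prescribed within the past year". Staff are then told: "Record Name, dose and number of prescriptions within the past 12-months for all" inhaled medications.

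**Re-screening.** Section 4.3 allows it once the reason for failure has resolved, with one exception: "This does not apply to cases where screen failure is related to SABA-use during the prior 12-months being below the threshold for study inclusion".

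**Spirometry.** Table 4 has "SFP1: If FEV-1/FVC ratio >0.7 on screening spirometry", while section 4.1 requires a ratio below 0.7.

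**Progression limits.** Section 12.2 sets overall recruitment at green from 6.5 per month and red below 5. The synopsis plans 80 patients over 12 months.

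**The concern.** High SABA use defines the trial population. If the inclusion list and the screening list classify the same patient differently, staff who follow Table 4 will turn away people whom section 4.1 admits.

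Three outputs of the feasibility trial depend on this. The first is the recruited population itself. The second is the count and pattern of screen failures, which is a feasibility outcome in Table 3. The third is the baseline mean and variability of SABA use: objective 2 in section 2 exists to supply that variability for the Phase-3 sample size, and daily users may differ from most-days users in both level and spread. A variance estimated in one population and applied to a Phase-3 trial recruiting the other could mis-size that trial.

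**Working it through.** No sample size or power figure is involved. The check sets the rules side by side and runs plausible patients through them.

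**1. Frequency.** Let D be self-reported days of use per week.
- Synopsis and sections 4 and 4.1: eligible if D ≥ m, where m is the cut-off for most days. The protocol does not give m; I take 4.
- SFP5a: screen failure if D < 7.
- The rules conflict for every D from m to 6. The conflict disappears only if most days means all seven. The protocol does not use the words that way: the hand-held fan question in Table 4 offers every day and most days as separate answers.

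**2. Unit.** Let R be prescriptions in the year and k inhalers per prescription, so inhalers N = R × k.
- Section 4 footnote: R ≥ 12.
- Synopsis, section 4.1 and SFP5b: N ≥ 12.
- If k = 1, the rules agree. If k = 2, they disagree for R = 6 to 11 (N = 12 to 22).
- The protocol neither gives k nor equates a prescription with an inhaler. Table 4 applies a rule on N but asks staff to record R, so the recorded item cannot confirm the rule unless k is known.

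**3. Patient profiles** (assuming m = 4, daily = 7, k = 1 or 2):

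| R × k | N | D | Section 4 | Section 4.1 | Table 4 |
|---|---|---|---|---|---|
| 12 × 1 | 12 | 7 | in | in | in |
| 12 × 1 | 12 | 6 | in | in | fail (SFP5a) |
| 12 × 1 | 12 | 5 | in | in | fail (SFP5a) |
| 6 × 2 | 12 | 7 | out | in | in |
| 6 × 2 | 12 | 5 | out | in | fail (SFP5a) |
| 11 × 1 | 11 | 7 | out | out | fail (SFP5b) |

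Rows 2 and 3 need no assumption about k. Rows 4 and 5 need k = 2.

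**4. Recruitment headroom.** Planned rate: 80/12 = 6.67 per month. Distance to the green limit: 6.67 − 6.5 = 0.17 per month, and 0.17/6.67 = 2.5%. Over the year the green limit is 6.5 × 12 = 78, two participants below target. The red limit is 5 × 12 = 60. These figures give the margin only; the loss due to SFP5a cannot be calculated.

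**5. Canister conversion.** Section 6.2.2 equates 7 actuations per day with about 12 canisters of 200 per year. This reproduces: 7 × 365/200 = 12.8. In reverse, 12 × 200/365 = 6.6 actuations per day.

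**The case against.** **The rules overlap.** A daily user with 12 prescriptions passes all of them, and sections 4.1 and SFP5b agree on inhalers or canisters. A reader might infer three mutually exclusive definitions; the text does not support that. Section 4 and Table 4 are each narrower than section 4.1, in different directions. The frequency conflict stands without any assumption about prescribing, whereas the unit mismatch matters only where a prescription carries more than one inhaler.

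**Few patients may be affected.** Someone prescribed 12 canisters a year averages 6.6 actuations a day if all are used, so many will be daily users. Prescribing is not use, so this does not settle the share, but it argues against assuming a large one.

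**Recruitment need not fall in proportion.** A reader might infer that the wording alone takes recruitment to amber or red. The documents do not support this: 80/12 is a target rather than an observed rate, screen failures are replaced (sections 4.3 and 7.1.3), and neither the eligible pool nor site capacity is given. Consent also precedes screening, so the direction of any change in the eligibility to consent ratio is not established.

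**An SFP5a failure is not clearly permanent.** The bar in section 4.3 concerns use over the prior 12 months below a threshold. The only criterion with that window is the count of 12, so the bar clearly covers SFP5b but not SFP5a.

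**Sites and arms.** A reader might expect sites to split between the two texts and so become non-comparable. Nothing indicates this; there is one protocol and one central eCRF. Randomisation follows confirmation of eligibility and is stratified by site, so the conflict gives no reason to expect bias between arms.

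**Spirometry at exactly 0.70.** This is not a true gap: section 4 makes anyone missing a criterion ineligible, so 0.70 is already excluded. Only the sign in SFP1 is out of step.

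None of this removes the direct contradiction between most days and daily.

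**Conclusion.** The frequency criterion contradicts itself. A patient who reports using SABA 5 or 6 days a week is eligible under the synopsis and sections 4 and 4.1, and a screen failure under SFP5a. The conflict holds for any reading of most days short of all seven. Following Table 4 as written removes such patients, adds to the screen failures, and restricts the baseline SABA data to daily users.

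The size of the effect on enrolment cannot be derived because the share using SABA on most but not all days is not stated. A lower recruitment rate is possible, and the margin to the green limit is only 2.5%, but no projected rate or change of traffic-light colour follows from the documents.

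The unit mismatch is secondary and conditional on more than one inhaler per prescription. Where that applies, a patient failed for counting the wrong unit cannot be re-screened. The SFP1 sign is a minor tidy-up.

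**What to change.** 1. Choose one frequency and one unit. The choice is for the trial team; what matters is that a single definition appears word for word in the synopsis, sections 4 and 4.1, SFP5a and SFP5b in Table 4, and the eCRF.
2. Make the screening form record the unit that the rule counts. If that is inhalers or canisters, recording the number of prescriptions alone is not enough.
3. Re-review any screen failures already recorded under SFP5a or SFP5b against the reconciled definition.
4. Align SFP1 with the section 4.1 limit so that a ratio of 0.70 is recorded as a screen failure.

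The cost is a protocol wording change, an eCRF edit, a short note to sites and the review of existing failures. No extra participants or visits are needed.
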